10.6 Follow-up Phase

10.6.1 Phone Call

Each subject will be contacted by phone within 48 hours after completion of desaturation phase to perform a safety assessment. The safety assessment will include asking the subject the following questions:

- Have you had any medical problems since your discharge from the clinical research unit?
- Have you taken any medications (either prescribed or self-medicated) since discharge from the clinical research unit?

For more details on AE, refer to *Section 12*.

10.7 Assessment of Safety

Safety analysis will be performed on all participants who will have the NIRS sensors placed on the forehead or any sensor placed on somatic sites. Methods and timing for assessing, recording, and analyzing safety parameters, including adverse events are described in *Section 12* and *Section 14*.

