- 5) Subject's Skin tone will be evaluated and recorded (e.g. light, medium, and dark) will be evaluated and recorded on provided study eCRFs.
- 6) Blood pressure (BP) and Heart rate (HR) will be recorded at enrollment visit 1. BP and HR continuously will be monitored during desaturation phase.
- 7) Jugular bulb and arterial catheters will be inserted for each subject. Jugular bulb catheter will be placed under ultrasound guidance and placement will be verified with a single lateral skull x-ray. The tip of the jugular catheter should be positioned cephalad to the inferior border of the first cervical vertebrae (C1) to minimize the risk of jugular venous blood mixing with extra-cranial effluent venous drain. Side and location of the catheters will be recorded in the study provided eCRFs.
- 8) Two investigational NIRS sensors will be placed on the forehead.
- 9) Two sensors (investigational and legacy) will be placed on somatic site (e.g. calf) of the subjects.
- 10) De-identified images may be taken on the locations before and after sensor application(s).
- 11) Each subject will complete a series of Desaturation Sequence steps (#1-18) with incremental reduction/increase of SpO₂ to target ranges between 70-100%. Each subject will complete three Desaturation Sequences (████████). For more details, refer to *Section 10.5*.
- 12) The arterial (SaO₂) and venous (SjvO₂) blood draws will be repeated to target two paired samples per step. A total of █ paired arterial and venous draws (pair = 1 jugular: 1 arterial) will be collected during the study. The jugular sample will be drawn approximately over a period of █ seconds (████████). For more details, refer to *Section 10.5*.
- 13) Information will be collected throughout the study with starting Visit 1, Enrollment Phase and through Follow-up Phase. Adverse Event assessment for the purposes of this study will cease

This document is electronically controlled. Printed copies are considered uncontrolled.

Confidential MDT16010MAVJB3	████████	████	████
---------------------------------------	----------	------	------

after follow-up phone call within 48 hours after desaturation visit. All Adverse Events, regardless of relatedness or outcome, must be reported. For more details, refer to *Section 12*.

- 14) The local laboratory will be used for all laboratory assessments.
- 15) Hemoglobin electrophoresis is used to identify variant and abnormal hemoglobin.

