10.4.2 Visit 2A (Study Day)

- On the study day, subjects will arrive at the clinical research unit with appropriate fluid and solid intake as directed by study staff.
- Any significant change in health status since Visit 1 will be recorded.
- Concomitant Medications: All subjects will have urine drug screen and alcohol breathalyzer (Oral Ethanol) tests done.
- Female subjects will also have a urine pregnancy test done.
- Inclusion and Exclusion Criteria will be reviewed.
- Enrollment Pass is based upon successful meeting all of inclusion and none of exclusion criteria during Visits 1 and 2A.

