Any complaint should be reported to the Medtronic research contact below **as soon as possible, but no later than 10 working days** after the investigator first learns of the effect. If an event occurs on late Friday evening, or if office is closed due to long holidays or for any other reasons, the event will be reported the following working day.

Emergency Contact Information

13 Data Review Committees

Not applicable.

14 Statistical Design and Methods

Statistical analyses will be conducted by Medtronic or its designee as outlined in the Statistical Analysis Plan (SAP). Any changes in statistical methods will be detailed in the SAP.

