14.2 Statistical Analysis

Briefly, standard demographic information and baseline characteristics data will be summarized using descriptive statistics.

For safety assessments, adverse events (AEs) will be summarized using frequency counts and percentages. Descriptive statistics will be provided by severity and relationship.

Individual listings of adverse events, including event type, start date, duration, severity, and device-relatedness will be provided as appropriate. The safety analysis will be based on all patients participated in the study.

The effectiveness analysis will be based on all evaluable data from this study. A per protocol analysis will be performed based on all subjects who are compliant with the study protocol, i.e. who provide valid informed consents and participated in the desaturation phase.

INVOS rSO₂ values will be compared to the calculated global field saturation of brain tissue (25% arterial saturation + 75% jugular venous saturation). The arithmetic root mean square (A_{RMS}), systemic bias, and standard deviation will be calculated for both individuals and pooled data.

Pearson linear correlation coefficient will present the strength of the linear correlation between fSO₂ and rSO₂. Bland-Altman analysis with limits of agreement will assess agreement between rSO₂ and fsO₂ with

This document is electronically controlled. Printed copies are considered uncontrolled.

multiple observations per individual. Any deviations from the original statistical plan will be justified and documented appropriately.

15 Ethics

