#### 7.1.3. Analysis Sets

Subjects will be considered enrolled in the study once it has been confirmed that they meet all the inclusion and none of exclusion criteria. Unless otherwise specified, analysis of reported outcomes will include all available data for all subjects enrolled.

This document is electronically controlled. Printed copies are considered uncontrolled.

Confidential MDT16010MAVJB3	[REDACTED]	[REDACTED]
--------------------------------	------------	------------

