**7.9. Safety Evaluation**

Adverse events for all enrolled subjects will be collected and reported. Summary of overall event, events relatedness, seriousness and severity will be provided. To assess safety, the number and percentage of subjects with adverse events will be summarized by severity. And the total number of events will be provided as well.

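### Protocol 10.7 ties the safety analysis to sensor placement, conflicting with the SAP's all-enrolled set; if followed, it would leave failed catheter insertions out of the safety tables

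*Protocol*

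**What the plan says.** Three descriptions of the safety population stand in the current text.

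- Protocol 10.7: "Safety analysis will be performed on all participants who will have the NIRS sensors placed on the forehead or any sensor placed on somatic sites". Its next sentence begins "Methods and timing for assessing, recording, and analyzing safety parameters, including adverse events are described in" and points to Sections 12 and 14, so it states one set and sends the reader to another.
- Protocol 14.2, and the synopsis under Statistics: "The safety analysis will be based on all patients participated in the study". Neither place defines participation.
- SAP 7.9: "Adverse events for all enrolled subjects will be collected and reported". SAP 7.1.3 defines the term: "Subjects will be considered enrolled in the study once it has been confirmed that they meet all the inclusion and none of exclusion criteria". Protocol 9.2 defines enrollment in the same way.

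On precedence, Protocol 14 opens: "Statistical analyses will be conducted by Medtronic or its designee as outlined in the Statistical Analysis Plan (SAP"). No sentence says that the SAP overrides 10.7.

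On timing, Protocol 10.4.2 says: "Enrollment Pass is based upon successful meeting all of inclusion and none of exclusion criteria during Visits 1 and 2A". Visit 2B, with catheters and study sensors, comes after that point.

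**The concern.** SAP 7.9 plans numbers and percentages of subjects with adverse events. A percentage needs one denominator, and the documents give three descriptions of it, which do not select the same people.

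The group that matters is subjects who pass enrollment, go to catheterisation at Visit 2B, and are withdrawn because access cannot be obtained. Protocol 10.10 lists this as a reason for withdrawal, so the sponsor foresees it. These subjects have been exposed to the insertion attempt. Protocol 11.1.2.1 places most jugular catheter complications at that step and names carotid puncture, pneumothorax and nerve injury among them. A safety set that starts at sensor placement would count these subjects in neither numerator nor denominator, and the tables would understate events from the invasive part of the procedure.

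**Working it through.** There is no figure in the plan to reproduce. The check sets the passages side by side and follows one subject through them.

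**Step 1: is a failed-access subject enrolled?** Enrollment is eligibility confirmed (SAP 7.1.3, Protocol 9.2). Enrollment Pass follows Visits 1 and 2A (Protocol 10.4.2), and catheters are inserted at Visit 2B, after the pass (Protocol 10.5.1). So yes.

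**Step 2: has that subject had a study sensor placed?** The synopsis, Protocol 7 and Protocol 10.5.1 all list the catheters first and the sensors afterwards. If that order is followed, a subject withdrawn at the catheter step has no Visit 2B sensor. The order is inferred from consistent listing; no sequence rule is stated.

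**Step 3: which sensors does 10.7 mean?** Two readings are possible.

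- Natural reading: the Visit 2B sensors. Footnote 8 to Table 1 uses the same term for the investigational pair: "Two investigational NIRS sensors will be placed on the forehead". Protocol 10.7 also pairs the forehead sensors with somatic sensors, which Table 1 schedules only at Visit 2B.
- Literal alternative: any NIRS sensor on the forehead. Visit 1 includes a forehead baseline reading with the cleared INVOS 5100C (Protocol 10.4.1), and Protocol 8.1 calls that device a NIRS system. Then almost everyone who reaches Visit 1 is in the set.

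**Step 4: who is in each set?**

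| Subject | 10.7, natural reading | 10.7, literal alternative | SAP 7.9 with 7.1.3 | Synopsis and 14.2 |
|---|---|---|---|---|
| Enrolled, study sensors placed | in | in | in | in |
| Enrolled, access failed before sensors | **out** | in | in | unclear; probably in |
| Consented, failed screening after the Visit 1 forehead reading | out | in | out | unclear |

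The second row is the contradiction. Membership depends on the section used and, within 10.7, on how one term is read.

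**Step 5: size.** The documents give no number of failed insertions and no expected event count. To show only how the table entry changes, assume the maximum of 50 enrolled (Protocol 14.1), *k* failed-access subjects with one insertion event each, and no other events.

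- Enrolled set: *k*/50. For *k* = 1, 1/50 = 2%. For *k* = 5, 5/50 = 10%.
- 10.7 set, natural reading: 0/(50 − *k*). For *k* = 1, 0/49. For *k* = 5, 0/45. Both are 0%.

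The values of *k* are assumptions. What changes is whether the events appear in the table at all.

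**The case against.** The strongest reply is that the plan already resolves the conflict. Protocol 14 sends the analysis to the SAP, 10.7 itself points to Section 14, and the SAP set keeps failed-access subjects. On an ordinary reading, someone catheterised at Visit 2B has also participated. That leaves one sentence in a procedures section against the statistics section, the synopsis and the SAP. The sentence also lacks the word *only*, and it excludes anyone only on the natural reading of the sensor term and the inferred order of procedures.

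Most of this stands, and it limits the point to a wording conflict. It does not remove it: the 10.7 sentence remains in the protocol, nothing says it yields, and its meaning depends on the reader.

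Three stronger inferences are tempting and are not supported.

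- *Insertion events will be lost to the study.* They will not. Protocol 12.2 collects adverse events from Visit 1 and requires them to be reported to the sponsor regardless of relatedness. Only the safety tables and denominators are at issue.
- *The SAP set is itself wrong because it omits consented subjects who fail screening after the Visit 1 blood draws and 15% oxygen mask test.* Summarising safety in enrolled subjects is a defensible choice and agrees with Protocol 9.2. Starting collection at Visit 1 does not oblige the plan to put screen failures in the denominator, and their events still go to the sponsor.
- *The study's main conclusions are affected.* The primary objective concerns cerebral accuracy and trending, and the safety analysis is descriptive with no hypothesis test.

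**Conclusion.** The point holds as a contradiction between Protocol 10.7 and SAP 7.9 with 7.1.3, with an undefined third wording in the synopsis and Protocol 14.2. If 10.7 is followed on its natural reading, enrolled subjects withdrawn for failed arterial or jugular access drop out of the safety tables, and with them the insertion complications that the protocol itself treats as the usual kind. If the SAP is followed, they stay in.

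The conclusion that 10.7 excludes them rests on two readings: that its sensors are those of Visit 2B, and that catheters precede sensors. The need to reword does not rest on either, because a set whose membership changes with the reading is not fit for a denominator. The size cannot be computed from the documents. The correction should be made before the safety tables are produced.

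**What to change.** Replace the 10.7 sentence, and the participation wording in the synopsis and Protocol 14.2, with the SAP set: all enrolled subjects, expressly including every subject in whom catheter insertion was attempted, whether or not a sensor was then placed. Repeat the definition in SAP 7.9.

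Report two further denominators: subjects with insertion attempted, for catheter events, and subjects with a study sensor placed, for device-related events. Neither rate is then diluted by subjects who were not exposed.

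As an optional addition, not the correction of an error, list separately any adverse events from Visit 1 or 2A in consented subjects who fail screening, since collection starts at Visit 1. Because Protocol 10.8.2 describes eCRFs for enrolled participants, state how those events reach the listing.

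The cost is wording edits and two extra denominators. No procedure, visit or sample size changes.

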10.8 Recording Data

10.8.1 Source Documents

The investigator will clearly mark the clinical records to indicate that the subject is enrolled in this clinical study.

Subject's medical record will be used as part of source documents. Source documents are all information, original records of clinical findings, observations, or other activities in a clinical trial necessary for the reconstruction and evaluation of the trial. Source data are contained in source documents. Adequate original records will be maintained for the study. Examples of these original documents and data records include: ICF, all events, hospital records, clinical and office charts, laboratory notes, memoranda, evaluation checklists, device dispensing records, collected records, copies or transcriptions certified after verification as being accurate and complete, radiology files (ultrasounds, X-rays), informed consent form, and records kept at the laboratories and at medical-technical departments involved in the clinical trial.

In order to accurately collect all study data, worksheets/ forms may be developed for study specific data not found in the medical records and will be considered as the source document for these data points.

The device (investigational and non-investigational) use (disposition) for the individual subject during this trial will be recorded directly on the study provided eCRF page and will be considered as source data. The copy of device disposition eCRF page will be printed and left at the site as the source document.

This document is electronically controlled. Printed copies are considered uncontrolled.

Confidential MDT16010MAVJB3			
---------------------------------------	--	--	--

10.8.2 Case Report Forms

The electronic Case Report Forms (eCRFs) will be utilized for participants enrolled in the study. The appropriate eCRF will be completed by the site within a target of 5 business days after each study examination. All data requested on the eCRF must be recorded or the entry will be queried.

The investigator must ensure accuracy, completeness, and timeliness of the data reported in the eCRFs and in all other required reports. Data reported on the eCRFs, which are derived from source documents, such as patient medical records, must be consistent with the source documents or the discrepancies need to be justified in a documented rationale, signed and dated by the Principal Investigator (PI), to be filed in the subject file.

Training will be provided to site personnel on the use of data collection tools. The final version of eCRFs will be provided to the investigation sites when the investigational site has been declared ready for the study.

All clinical data generated in the study will be submitted to Medtronic for quality assurance review and statistical analysis. All eCRFs will be reviewed for completeness and evident errors. Questions or queries will be resolved by contact with the clinical sites.

Sponsor study personnel will review collected data and create data queries for missing data that impacts data analysis. Queries will be sent to the investigator or appropriate support staff for resolution.

10.9 Deviation Handling

10.9.1 Deviations

The investigator is required to conduct this study in accordance with the protocol, Good Clinical Practice (GCP), Institutional Review Board (IRB) requirements, and applicable regulations.

A study deviation is defined as an event when the investigator or site personnel did not conduct the study according to the protocol or the clinical trial agreement.

The investigator is required to obtain prior approval from the sponsor and IRB *before* initiating deviations from the study protocol, except where necessary to protect the life or physical well-being of a subject in an emergency. Such approval will be documented in writing and maintained in the study investigator files.

Major deviations are defined as deviations with respect to:

- Patient informed consent procedure;
- Patient eligibility criteria;
- Study data collection and reporting;
- Serious Adverse Event /Serious Adverse Device Effect /Unanticipated Adverse Device Effect /Unanticipated Serious Adverse Device Effect reporting (*for reporting refer to Section 12*).

All deviations and reasons to deviate from the study protocol must be reported to the Sponsor as soon as a possible, but **no later than 5 working days** of the protocol deviation.

This document is electronically controlled. Printed copies are considered uncontrolled.

Confidential MDT16010MAVJB3			
---------------------------------------	--	--	--

The Principal Investigator is responsible for reporting the protocol deviation in accordance with the policies and procedures established by the IRB.

10.9.2 Informed Consent

If an investigator uses a device without obtaining informed consent, the investigator shall report such use to the sponsor and the reviewing IRB **within 5 working days** after the use occurs.

The sponsor shall submit to FDA a copy of any report by an investigator of use of a device without obtaining informed consent, within 5 working days of receipt of notice of such use.

10.10 Subject Withdrawal or Discontinuation

Subjects may withdraw from the study at any time and for any reason. If a subject officially withdraws from the study, the reason for withdrawal will be documented.

Possible reasons for withdrawn from the study are:

- Subject withdrew consent;
- Investigator withdrew subject from the study for medical reasons;
- Investigator withdrew subject from the study due to failure to maintain adequate compliance;
- Investigator withdrew subject from the study due to inclusion/exclusion criteria not met.
- Investigator withdrew subject from the study due to an inability to establish arterial and/or jugular lines.
- Investigator withdrew subject from the study due to the occurrence of slurred speech, confusion, somnolence, fainting, or other alteration of the mental status of the subject.

Following terms are used for withdrawal and completion:

- *Enrollment Withdrawal:* Removal from study prior to Desaturation Phase; initiated by either by subject, sponsor or PI (Visits 1 or 2A);
- *Study Withdrawal:* Removal from the study after Enrollment Pass;
- *Study Incomplete:* Completion of some study related activities by the subject in Visit 2B;
- *Study complete:* Completion of all study related activity by the subject in Visits 1 and 2, and Follow-up phone call. Desaturation Phase, Visit 2B, is considered complete if Sequence #1 or #2 are completed. Completion of all Sequences #1, #2, and #3 are desirable, but not considered incomplete, should subjects withdraw for any reason;
- *Lost to follow up:* Subjects lost to follow-up will be documented. The investigator should make every attempt to contact the subject to have the subject complete the follow-up phone call within 48 hours or to determine the occurrence/resolution of adverse events (if any).

This document is electronically controlled. Printed copies are considered uncontrolled.

Confidential MDT16010MAVJB3			
---------------------------------------	--	--	--

11 Risks and Benefits

11.1 Potential Risks

Risks to participation are primarily physical. There are no social, economic, legal, long-term psychological or other risks that have been identified. Risks under this protocol relate to both study devices and study procedures. We believe that the risks from the device(s) are in keeping with the definition of non-significant risk devices (NSR) (See *Section 11.3*). Further, the devices in this study are non-invasive and the clinical protocol design is minimal risk to the subject. No treatment or treatment decisions will be made during the course of this study. Following is a list detailing potential risks from study devices and the clinical protocol.

11.1.1 Investigational Devices

11.1.1.1 Sensors/ Preamplifiers/ Monitor

Term	Percentage
GDP	100
Inflation	98
Interest rates	97
Central bank	96
Monetary policy	95
Quantitative easing	94
Inflation targeting	93
Interest rate hike	92

11.1.2 Clinical Protocol/ Procedural Risks

11.1.2.1 Arterial and Jugular Bulb Catheters

Complications of jugular bulb catheter insertion/monitoring are uncommon and usually related to catheter insertion. Placement of an arterial or venous catheter is often uncomfortable, even with local anesthesia. The risks common to arterial and venous catheter placement are those associated with any vascular catheter. These include pain, bleeding, hematoma, infection, thrombosis and embolism. Complications with internal jugular bulb catheterization include carotid artery puncture, pneumothorax, nerve injury, infection, thrombosis [4] hemomediastinum, hydromediastinum, hydrothorax, and vessel perforation/damage and catheter embolism. The insertion complications will be reduced by inserting the catheter under ultrasound guidance. In the case of accidental arterial puncture, local pressure will be

This document is electronically controlled. Printed copies are considered uncontrolled.

Confidential

MDT16010MAVJB3

applied to the site. Drawing of the venous sample will be done under careful slow draw to avoid collapsing of the jugular bulb structure.

Radial arterial cannulation is used often in appropriate patients during clinical care. Major complications rates are rare and <1%. [7] Complications of arterial catheters include trauma at the insertion site, catheter-related difficulties, bleeding, and hematomas. More severe complications, which occur less frequently include phlebitis, infection, sepsis, radial artery aneurysm, thrombosis, abscess formation, cellulitis, paralysis of the median nerve, air embolism, compartment syndrome, carpal tunnel syndrome, occlusion with local and distal ischemia and loss of hand. The use of an aseptic cannulation technique performed by clinicians who have extensive experience and the short duration of catheterization will minimize these risks. Subjects are counselled to avoid strenuous wrist activity after removal of the catheter to minimize for hematoma formation and bruising.

